7.3 Method of Assigning Patients to Treatment Groups

The CROs will prepare the randomization scheme in accordance with its SOPs and the randomization plan, which reflect GCP standards. Refer to [Section 10.3](#) for a description of

randomization methods. Eligible patients will be assigned to a treatment group according to the list of patient randomization assignments.

7.4 Measurements of Treatment Compliance

Study drugs will be administered by delegated and trained staff at the CRUs. Details regarding dosing, including the dose administered and the date and time of dosing, will be recorded.

7.5 Study Drug Storage, Accountability, and Retention

7.5.1 Storage Conditions

The investigator will ensure that all the study drugs are stored and dispensed in accordance with the regulations from the regulatory authority concerning the storage and administration of investigational drugs.

LT5001 drug product will be stored at controlled room temperature ($\leq 25^{\circ}\text{C}$) in the original packaging.

7.5.2 Drug Accountability and Retention

The investigators must ensure that all study drug supplies are kept in a secure locked area with access limited to those authorized by the investigator. The investigator must maintain accurate records of the receipt of all study drug shipped by Lumosa Therapeutics Co., Ltd. or their representative, including but not limited to the date received, lot number, expiration date, amount received, and the disposition of all study drug. Current dispensing records will also be maintained including the date and amount of study drug dispensed and the patient receiving the drug. All remaining study drug not required by regulations to be held by the CRU must be returned to Lumosa Therapeutics Co., Ltd. or their representative immediately after the study is completed.

7.6 Packaging and Labeling

7.6.1 Study Drug

[REDACTED]

7.6.2 Blinding of Treatment Assignment

The CRO will maintain the randomization code in a secure location with controls to prevent unauthorized access, including the computer program written to generate the randomization, randomization codes, program log, seed number used by the program, copy of the randomization plan along with approval documentation as appropriate, and the write-protected electronic storage medium.

The site and CRO will name an unblinded statistician to provide the randomization code. Investigators, pharmacists, site staff, patients, CRO, and the Sponsor will remain blinded to individual patients' treatment assignment for the duration of the study until the study unblinding has been authorized.

In order to preserve the blind, study drug will be prepared and administered in a manner that masks the content for both the patient and staff member administering the drug.

7.6.3 Unblinding of Treatment Assignment

7.6.3.1 Unblinding for Adverse Event/Safety Reasons

Should an SAE or other circumstance require that the blind be broken to ensure patient safety, the investigator must immediately notify the medical monitor. The medical monitor will notify the Sponsor as soon as possible and will release the treatment assignment of the patient to the appropriate personnel in accordance with the applicable study-specific procedure.

If the treatment assignment is unblinded by the site pharmacist or any party other than CRO, the investigator must notify CRO in writing and document the course of events in the source records. Any patient for whom the treatment code is prematurely released will be withdrawn from the study.

7.7 **Concomitant Medications & Procedures/ Prohibited medication/ Other Restrictions**

7.7.1 Concomitant Medications

Concomitant medications during the study will be documented on the concomitant medication eCRF. Information recorded will include: start and stop dates and times, dose and route of administration, and indication.

- **Allowed concomitant medication**

Concomitant medications or vaccinations may be administered if they are prescribed or confirmed by the investigator for the treatment of specific clinical events. When possible, the Sponsor will be consulted before administration of concomitant medications.

Maintenance medications as prescribed by the patient's physicians are permitted.

- **Allowed but need to maintain stable treatment regimen**

After signing informed consent, subjects may continue previous antipruritic therapy prescribed by their physician throughout the study (unless specified in the prohibited

medication [Section 7.7.3](#)), including but not limited to oral antihistamine agents and corticosteroids. The antipruritic regimen must maintain stable (defined as no change in prescription) throughout the study.

Medications for the management of serum phosphorus, calcium, or iPTH is recommended to maintain stable unless are permitted by the subject's physician for the treatment of specific clinical events. .

7.7.2 Concomitant procedures

No concomitant procedures other than dialysis will be performed during the study unless approved by the investigator. Medications taken for a procedure will also be included on the concomitant medication eCRF, as well as the procedure itself.

7.7.3 Prohibited medication

Gabapentin, pregabalin, and topical antihistamine/ corticosteroids are prohibited throughout the study. Administration of OTC antihistamine and corticosteroids for antipruritic treatment are also not allowed.

7.7.4 Other Restrictions

Patients will be instructed to adhere to the following restrictions:

- Patients are not permitted to participate in any other clinical trial or donate blood or plasma while participating in this clinical trial.

8 STUDY ASSESSMENTS AND PROCEDURES

Patients will undergo study procedures and assessments at time points specified in the schedule of assessments (Table 2.1, Table 2.2, and Table 2.3)

8.1 Diary run-in (7-days itch NRS)

Subject need to record the daily worst itching intensity NRS for 7 days in the patient diary at screening. At least 6 of 7 itch NRS must be completed and the mean NRS score > 4 to be qualified for participation in the study.

After signing informed consent, a patient diary will be provided to the subject for the Diary run-in procedure at screening. Patient eligibility will be confirmed after completion the study procedures specified in the schedule of assessment. In practice, the order of the procedures should be: (1) obtain informed consent (2) review inclusion and exclusion criteria (3) Diary run-in and all other assessments for screening indicated in the schedule of assessments ([Table 2.1](#), [Table 2.2](#)) (4) confirm eligibility (5) randomization.

8.2 7-days Repeated open application tests (7-days ROAT)

In the first 7 days of study treatment, subject will need to undergo a 7-day repeated open application tests (ROAT). A 0.5 fingertip unit of the study drug is recommended to apply to a $5 \times 5 \text{ cm}^2$ fixed pre-marked zone without any skin lesions near the antecubital fossa twice daily in the morning and evening for 7 days. If skin lesion is occurred in the antecubital fossa, it is acceptable to choose the volar forearm or ventral inner arm without skin lesion under the judgment of investigator to perform ROAT (avoid the area depicted in the Section 7.2 Treatments Administered).

During the 7-days ROAT, the pre-marked zone applied with the study drug will be examined and assessed by ICDRG scale in each visit (details in [Section 8.8.6 Application Site Examination](#)). In the event of ICDRG $\geq +$ that is considered clinically significant will be recorded as AE. The investigator may photograph the skin condition if the investigator considered helpful for the safety assessment in the DSMB meeting (optional).

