5.1.1 Interim Safety/ Pharmacokinetic Data Review

Subject will receive application site examination at each visit (Part A: Visit 2 to 8; Part B: Visit 2 to 9) assessed by the trained study team, using ICDRG scale. If subject experience a new or worsening localized skin reaction in the treatment area, the subject should report to the study coordinator and/or investigator during the visit. Baseline skin condition conducted at screening in the physical examination should be used as a reference for comparison. All AEs should be recorded in the eCRF

If a subject experience 1 newly arise acute inflammation of the skin (e.g. pain, transient erythema, vesiculation, severe swelling with bullae, ulceration, or even both) at the application site, and is related (at least possible) with study drug, study treatment is recommended to be interrupted. Upon resolution of the acute inflammation, subject may resume study treatment upon investigator's judgment.

After completion of 18 subjects in Part A, the DSMB will convene to review all safety and PK data. Part B will only occur if the DSMB determines that the current dose was safe and well-tolerated. Doses for Part B will be decided by the DSMB after their review of the cumulative safety data targeted for review (AEs, vital signs, clinical laboratory results, physical examination results, itch results, and application site examination results) and available PK data from Part A. Sponsor will make the final decision in an unblinded fashion.

An ad hoc DSMB meeting will be convened in the following situations:

1. In the event of 4 subjects experiencing drug related (at least possible) adverse events with at least moderate intensity after the 1st dose of study drug or any ICDRG grade of ROAT $\geq 1+$ found during the first 7 days of study treatment, ad hoc DSMB meeting will be held to review the safety data and recommend in writing to Sponsor whether to continue, modify, or stop the clinical study on the basis of safety considerations.

2. In the event of ≥ 2 subjects experiencing drug related (at least possible) adverse events with at least moderate intensity in the first 6 subjects receiving study drug after the 1st dose or any ICDRG grade of ROAT $\geq 1+$ found during the first 7 days of study treatment, ad hoc DSMB meeting will also be convened to discuss the safety events to recommend Sponsor whether to continue, modify, or suspension the enrollment of the study.

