8.8.6 Application Site Examination

Application Site Examination will be conducted at Visit 2 to 8 in Part A and Visit 2 to 9 in Part B as indicated in schedule of assessment ([Table 2.1](#), [Table 2.2](#)). Application site evaluation will be conducted by comparing the skin of the application site with the baseline skin condition in each visit.

The application site evaluation will include dermatitis, pruritus, paresthesia, erythema, dryness, vesicles, irritation, papules, burning assessed by ICDRG scale (Table 8.2). An abnormal application site finding that is considered clinically significant will be recorded as AE. The investigator may consider photograph the skin condition under the consent of the subject if the investigator considered helpful for the safety assessment in the DSMB meeting (optional).

Table 8.2 Grading score by International Contact Dermatitis Research Group (ICDRG)

Grading	Morphology	Interpretation
-	No reaction	Negative
±?	Erythema only, no infiltration	Doubtful reaction
+	Erythema, infiltration, possibly discrete papules	Weak positive reaction
++	Erythema, infiltration, papules, vesicles	Strong positive reaction
+++	Erythema, infiltration, confluent vesicles	Extreme positive reactions
Ir	Different types of reactions (dermatitis, paresthesia, dryness, burning)	Irritant reaction

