9 ADVERSE EVENTS

An AE is defined as any untoward medical occurrence in a patient administered a pharmaceutical product during the course of a clinical investigation. An AE can therefore be any unfavorable and unintended sign, symptom, or disease temporally associated with the use of a study drug, whether or not thought to be related to the study drug.

Each AE will be collected from the signing of the ICF until the follow-up/end-of-study visit. Adverse events that are identified at the last assessment visit (or the early termination visit) must be recorded on the AE eCRF with the status of the AE noted. All events that are ongoing at this time will be recorded as ongoing on the eCRF. If the Investigator indicates the AE is “probably”, “possibly”, or “definitely” related to the study drug, the AE must be followed until they are resolved or medically stable, or until reasonable attempts to determine resolution of the event are exhausted. The investigator should use his/her discretion in ordering additional tests as necessary to monitor the resolution of such events.

The procedures specified in [Section 9.4](#) are to be followed for reporting SAEs.

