10.4 Endpoints

10.4.1 Part A Primary Endpoint

- Nature and severity of AEs and number of patients with AEs.

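### Protocol Sections 8.2 and 8.8.6 set conflicting AE-recording rules for the ROAT zone, so clinically significant ±? or Ir reactions there could be missed from the Part A primary endpoint

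*Protocol*

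**What the plan says.** Section 8.2 of the protocol describes the ROAT. On the examination it says that "the pre-marked zone applied with the study drug will be examined and assessed by ICDRG scale in each visit", and points to Section 8.8.6 for details. Its recording rule follows: "In the event of ICDRG $\geq +$ that is considered clinically significant will be recorded as AE".

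Section 8.8.6 covers the application site examination and lists nine reactions to look for. Its recording rule carries no grade: "An abnormal application site finding that is considered clinically significant will be recorded as AE".

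Table 8.2, inside 8.8.6, holds the scale. The categories −, ±?, +, ++ and +++ form an order. ±? is "Erythema only, no infiltration", interpreted as doubtful. Ir, the irritant reaction, is a separate last row described as "Different types of reactions (dermatitis, paresthesia, dryness, burning".

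Two general provisions also bear on recording. Section 9 states: "An AE can therefore be any unfavorable and unintended sign, symptom, or disease temporally associated with the use of a study drug". Section 5.1.1 states: "All AEs should be recorded in the eCRF". Neither mentions an ICDRG grade.

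The Part A primary endpoint (Section 10.4.1) is "Nature and severity of AEs and number of patients with AEs". SAP 11.1 analyses it from recorded AEs and restricts the summaries to treatment-emergent events. SAP 11.6 separately tabulates the ROAT by ICDRG category, and its scale includes the doubtful and irritant categories.

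**The concern.** Two recording rules appear to cover the same skin. Under 8.8.6, clinical significance alone makes a finding an AE. Under 8.2, the sentence written specifically for the ROAT zone adds a grade of + or higher. If 8.8.6 already captures every clinically significant finding, the added grade has no effect unless it is meant to leave lower grades out. A site could reasonably take the specific sentence as the one that governs.

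At stake is what reaches the AE page. Local tolerability is part of the Part A primary objective (Section 4.1), and the ROAT is a dedicated local-tolerance test. A clinically significant reaction that stays off the AE page receives no intensity or relatedness grading as an AE and does not enter the treatment-emergent counts. It also cannot count toward the AE limb of the ad hoc DSMB triggers in Section 5.1.1. That limb counts subjects with at least possibly related AEs of at least moderate intensity: 4 subjects overall, or 2 or more among the first 6.

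**Working it through.** The plan gives no figure to reproduce on this point; Section 10.1 says no formal sample size calculation was made. The check is mainly a comparison of texts.

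**Step 1. Do both rules reach the ROAT zone?** Section 8.2 sends the ROAT examination to 8.8.6, and the zone is skin to which study drug is applied. On that reading, yes. If the ROAT zone were held to be outside 8.8.6, the conflict would be between 8.2 and the general AE definition in Section 9.

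**Step 2. Apply each rule to a ROAT-zone finding that the investigator judges clinically significant.**

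| Category in Table 8.2 | Section 8.2 read alone | Section 8.8.6 | Section 9 |
|---|---|---|---|
| ±? | below the named floor | record | no grade floor |
| +, ++, +++ | record | record | no grade floor |
| Ir | undefined: no rank against + | record | no grade floor |

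The rules agree for + and above. They diverge for ±?, and 8.2 gives no answer for Ir.

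**Step 3. How much falls in the gap?** Ir covers dermatitis, paresthesia, dryness and burning, which are 4 of the 9 reactions listed in 8.8.6. ±? covers erythema without infiltration.

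**Step 4. Would the ROAT limb of the ad hoc triggers catch these reactions?** That limb uses a grade of at least 1+, a label that does not appear in Table 8.2. If 1+ means +, then ±? falls below it and Ir is again undefined. A moderate, related Ir reaction left off the AE page would miss the AE limb and might not meet the ROAT limb.

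**Step 5. Size per patient.** Inputs: 12 LT5001 and 6 placebo patients (Protocol synopsis, Sample Size; SAP 3.1). For a patient with no other recorded AE, one omission changes the incidence of patients with AEs by 1/n:
- LT5001: 1/12 = 8.3 percentage points
- Placebo: 1/6 = 16.7 percentage points

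**Step 6. Who would be affected?** SAP 5.1 gives one site for Part A. One reading of 8.2 at that site could therefore apply to all 18 patients.

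**The case against.** The strongest reply is that the plan excludes nothing. Section 8.2 says when a ROAT reaction is recorded. It does not say only then, and it does not say that lower or irritant grades are not AEs. Its preceding sentence refers to 8.8.6, which requires recording without a floor, and Sections 9 and 5.1.1 point the same way. Omitting a clinically significant burning or dermatitis reaction would breach those provisions. This stands: the defect is a conflict that risks inconsistent recording, not an exclusion rule.

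A reader might also infer that Ir can never satisfy the 8.2 threshold. Table 8.2 does not support that. Ir has no stated rank and is listed after +++, so its status is undefined.

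A reader might infer that the local-tolerance signal would be lost to the DSMB. It would not. SAP 11.6 tabulates ROAT grades by treatment group, Section 5.1.1 puts application site results before the DSMB, and SAP 13 plans the interim for all data. Those tables do not, however, supply AE intensity or relatedness, or feed the treatment-emergent counts. The exposure is confined to those.

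Finally, it is tempting to attach a probability. With 12 patients and assumed reaction rates of 2%, 5%, 10% or 20%, 1 − (1 − r)^12 gives a 22%, 46%, 72% or 93% chance of at least one such reaction. The documents give no rate, and these are chances that a reaction occurs, not that it goes unrecorded. To move the incidence, the reaction must be graded only ±? or Ir, be judged clinically significant, be handled under 8.2 as if exclusive, and occur in a patient with no other recorded AE. Patients also treat itch areas at the same time, where 8.8.6 applies without dispute. To say that none would be recorded assumes the very reading in dispute.

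**Conclusion.** The concern holds as a conflict between two stated recording rules. Section 8.2 names a floor of + plus clinical significance for the ROAT zone; 8.8.6 and Section 9 have no floor. The protocol does not say which prevails or where Ir stands. A site that follows 8.2 literally could omit clinically significant ±? or Ir reactions from the Part A primary endpoint and from the AE limb of the ad hoc triggers.

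The size is 8.3 percentage points of LT5001 AE incidence per affected patient with no other recorded AE. How many patients would be affected cannot be derived from the documents. The conclusion rests on reading 8.8.6, through the cross-reference in 8.2, as covering the ROAT zone, and on a site being able to take the specific sentence as controlling. It does not show that the primary result will be understated. The matter is worth correcting because the affected counts are the primary endpoint and the remedy is simple.

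**What to change.** Reconcile 8.2 with 8.8.6 by removing the grade floor from the AE-recording sentence. Suggested wording: *Any ROAT-zone finding of any ICDRG category, including ±? and Ir, that the investigator considers clinically significant will be recorded as an AE.*

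This is a data-recording rule. It changes no dose, visit or procedure, and the SAP analysis needs no change because it works from recorded AEs. The 1+ label in the ad hoc DSMB triggers also needs reconciling with the categories in Table 8.2, including the standing of Ir; no threshold is proposed here.

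The cost is one protocol sentence. The downside is possibly a few more mild application-site AEs in the tables.

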8.3 Medical and Surgical History

The investigator or designee will collect a complete medical and surgical history within 3 months prior signing ICF at screening.

8.4 Demographic Characteristics

Demographic characteristics including sex, age, race will be recorded at screening.

8.5 Physical Measurements

Height (cm) and body weight (kg) (after hemodialysis) without shoes will be recorded. Body mass index will be calculated using the height obtained at screening.

8.6 Itch assessments

8.6.1 Daily Assessment of the itch intensity by the patient

Subjected will be instructed by the study personnel to daily self-record the itch intensity by NRS ([Appendix A](#)) in the patient diary in a fixed period. The following information will need to be documented during the study.

Diary run-in (7 days itch NRS):

- The daily worst itch NRS

From Day 1 to the end of study:

- The time of the drug administration
- The application site of the drug
- The daily worst itch NRS
- The time of the itch before the next dose administration
- The intensity of the itch before the next dose administration assessed by NRS

8.6.2 Questionnaire interviewed by investigator or designee

The Skindex-10 Scale and 5-D Itch scale are both multidimensional scales not only access pruritus intensity but measure the impact of pruritus on patients. The Skindex-10 evaluate how the patient's itch affects three important domains of quality of life including 3 domains (disease, mood/emotional distress, and social functioning) as noted in [Appendix B](#). Subjects filled one of seven bubbles ("0 [never bothered], 1, 2, 3, 4, 5, and 6 [always bothered]") for each of the questions. The total score was the sum of the numeric value of each answered question ranging from 0 to 60, with higher scores indicating worse itch-related quality of life. The 5-D itch scale include 5 domains (the duration, degree, direction, disability, and distribution) as noted in [Appendix C](#), with a total score ranging from 5 (no itching) to 25 (maximum severity).

The Skindex-10 and 5-D Itch scale will be performed when patients were in the dialysis unit. The investigator or designee will conduct a face-to-face interview to assist the subject complete the Skindex-10 Scale and 5-D Itch scale. Before the interview, the investigator or designee will be trained by the medical monitor to ensure the accuracy and maintain the consistency of the interview across individuals. Subjects will complete the questionnaire without input on the answers from the study team.

The questionnaire interview will be conducted every 2 weeks at day 1 (Visit 1), day 15 (Visit 5), and day 29 (Visit 7) in Part A, and day 1 (Visit 1), day 15 (Visit 3), day 29 (Visit 5), day 43 (Visit 7), day 57 (Visit 9) in Part B as noted in the schedule of assessments ([Table 2.1](#), [Table 2.2](#)).

In practice, the order of the procedures is recommended as follows but may be adjusted upon investigator's judgement: (1) Before dialysis: vital signs, blood sampling for the PK and

laboratory tests (2) During dialysis: Skindex-10 Scale and 5-D Itch scale (3) After dialysis: body weight, physical examination, and other safety assessment procedures.

